4.4 EFFICACY ANALYSES

For efficacy analyses, patients will be grouped according to the treatment assigned at randomization by interactive voice/web response system (IxRS), whether or not the assigned treatment was received.

The stratification factors will be the same as the randomization stratification factors (see Section 3.1); however, in order to minimize small strata sizes, only PD-L1 status (IC0/1 vs. IC2/3), nodal status (positive vs. negative) and tumor stage after surgical resection (\leq pT2 vs. pT3/pT4) will be used for stratified analysis purposes. Given the mechanism of action of atezolizumab, PD-L1 status will be used for the stratified analysis. Based on the prognostic significance (Protocol Section 3.3.5), prior neo-adjuvant chemotherapy (yes vs. no), and number of lymph nodes resected (< 10 vs. ≥ 10) will not be used for the stratified analysis. The eight strata will be applied to all time-to-event endpoints where stratified analyses are planned, including stratified log-rank test and stratified Cox regression model, unless otherwise specified.

Analyses based on stratification factors recorded on the electronic Case Report Form (eCRF) will also be provided if considerable discrepancy is observed between values from IxRS and eCRF records.

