3.3.5 Rationale for Stratification Factors

In order to balance the disease-related risk factors between the treatment arms, patients will be stratified at study entry. A stratified permuted-block randomization scheme will be used to obtain a balanced assignment to each treatment within levels of the stratification factors.

- Nodal involvement is considered to be a major prognostic factor for predicting disease recurrence and OS after cystectomy (Stein et al. 2001; Karakiewicz et al. 2006; Hautmann et al. 2012). The number of lymph nodes removed during cystectomy is prognostic as well (Herr et al. 2004).
- Pathological tumor stage is the most important independent prognostic variable for recurrence and OS for invasive bladder cancer. Comprehensive pathologic staging could be performed after cystectomy (with lymphadenectomy) (Stein et al. 2001; Shariat et al. 2006).
- Neoadjuvant chemotherapy has been added as a stratification factor to control for the potential differences in local standard care in major regions and for any differences in outcomes based upon the receipt of prior neoadjuvant chemotherapy.
- The level of PD-L1 expression by IHC has been shown to correlate with recurrence or OS in patients with UC (McDaniel et al. 2016; Bellmunt et al. 2015).

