6.4.1 Primary Efficacy Endpoint

The primary efficacy endpoint is investigator-assessed DFS, defined as the time from randomization to the time of first occurrence of a DFS event, defined as any of the following: local (pelvic) recurrence of UC; urinary tract recurrence of UC; distant metastasis of UC; or death from any cause. Data for patients without a DFS event will be censored at the last date the patient was assessed to be alive and recurrence free as determined with radiographic evidence. Data for patients with no post-baseline disease assessment will be censored at the randomization date.

For United States registrational purposes, the primary efficacy endpoint of DFS will be defined as described above with an additional censoring rule for missed visits. Data for patients with a DFS event who missed two or more scheduled assessments immediately prior to the DFS event will be censored at the last tumor assessment as determined with radiographic evidence prior to the missed visits. Type I error control (see Section 6.1.1) will be applied to this analysis of DFS.

DFS will be analyzed in the ITT population. The following analyses will be performed for both DFS endpoints described above. DFS will be compared between treatment arms using the stratified log-rank test. The hazard ratio (HR) for recurrence or death will be estimated using a stratified Cox proportional hazards model and the 95% CI for the HR will be provided. The stratification factors will be the same as the randomization stratification factors (see Section 4.2); however, stratification factors may be combined for analysis purposes if necessary to minimize small stratum cell sizes. Combination of stratification factors, if any, would be specified in the Statistical Analysis Plan (SAP) prior to analysis. The stratification factors will be obtained from the IxRS at the time of randomization. Results from an unstratified analysis will also be provided. Kaplan-Meier methodology will be used to estimate median DFS for each treatment arm; Kaplan-Meier curves will be produced. Brookmeyer-Crowley methodology will be used to construct the 95% CI for the median DFS for each treatment arm. The DFS rate at various timepoints (i.e., every 6 months after randomization) will be estimated by Kaplan-Meier methodology for each treatment arm, and the 95% CI will be calculated using Greenwood's formula.

The following additional analyses will be performed for both DFS endpoints described above:

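### Does leaving node count and prior chemotherapy out of the stratified analysis, with Protocol 3.3.5 cited as the reason, call for a change?

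*SAP*

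**What the plan says.** SAP 3.1 lists five two-level randomisation factors. SAP 4.4 keeps PD-L1 status, nodal status and tumour stage for every stratified time-to-event analysis. Its first reason is "in order to minimize small strata sizes". PD-L1 is kept because of the drug's mechanism. Prior chemotherapy and node count are left out "Based on the prognostic significance (Protocol Section 3.3.5").

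Protocol 6.4.1 foresees a reduction laid down in the SAP: "stratification factors may be combined for analysis purposes if necessary to minimize small stratum cell sizes". SAP 1 states that its analyses replace those of the protocol.

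Protocol 3.3.5 says of the retained factors:
- stage: "Pathological tumor stage is the most important independent prognostic variable for recurrence and OS for invasive bladder cancer"
- nodal status: "Nodal involvement is considered to be a major prognostic factor"

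Of the omitted ones it says:
- node count: "The number of lymph nodes removed during cystectomy is prognostic as well"
- chemotherapy: added to control for local practice and "for any differences in outcomes based upon the receipt of prior neoadjuvant chemotherapy"

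Both omitted factors are tabulated by arm (SAP 4.3) and are subgroup factors, with a hazard ratio within each level (SAP 4.4.5). SAP 4.4.1 adds an unstratified analysis. SAP 4.4 adds "Analyses based on stratification factors recorded on the electronic Case Report Form" if these differ considerably from the IxRS values, without naming which factors.

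**The concern.** Read literally, the SAP cites Protocol 3.3.5 as grounds for dropping two factors, yet that section calls one of them prognostic and calls neither non-prognostic. The citation appears to contradict its source.

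There is also a gap. The primary DFS and OS comparisons use the eight strata. The PD-L1 analyses (SAP 4.4.3.1) use the same factors minus PD-L1, and the weighted log-rank tests (SAP 4.4.3.3.2) use the 4.4 factors or none. Subgroup hazard ratios are unstratified and within level. None commits to a pooled treatment effect adjusted for node count or prior chemotherapy, although the trial chose to balance both. Chemotherapy also separates two eligibility groups with different stage thresholds (Protocol 4.1.1), so a reader may ask whether the result survives adjustment. At stake would be some efficiency and a robustness check, for OS as well as DFS.

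**Working it through.** **Design figure.** Inputs (SAP 2.2.2): medians 20 and 26.7 months, two-sided alpha 0.05, 80% power, 1:1. Schoenfeld: d = 4(1.960 + 0.842)² / (ln HR)². With HR = 20/26.7 = 0.749, d = 31.40/0.0835 = 376.1, so 377 as stated. At HR 0.75 exactly, 377 events give 79.8% power.

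**Why fewer strata.** Five binary factors give 2⁵ = 32 cells: on average 800/32 = 25 patients and 377/32 = 11.8 events. Eight strata average 100 patients and 47 events.

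**Simulated DFS power.** SAP accrual, 32% loss over 24 months, cutoff at 377 events and at least 12 months after last enrolment, HR 0.75, permuted blocks within the five-factor cells, Protocol 4.1.1 eligibility imposed; 30,000 trials per scenario. Assumed, because the documents do not give them: prevalence 50% (chemotherapy) and 25% (<10 nodes); retained-factor hazard ratios 0.85 (IC2/3), 1.8 (node-positive) and 1.7 (pT3/pT4).

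| Prognostic HR, chemotherapy / <10 nodes | 8 strata (SAP) | 8 strata + 2 covariates | 32 strata |
|---|---|---|---|
| 1.0 / 1.0 | 78.7% | 78.8% | 77.6% |
| 1.0 / 1.3 | 78.5% | 78.8% | 77.4% |
| 1.3 / 1.0 | 78.5% | 78.9% | 77.4% |
| 1.3 / 1.3 | 78.3% | 79.1% | 77.5% |
| 1.5 / 1.5 | 77.3% | 79.0% | 77.5% |

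Adjusted minus SAP: 0.1, 0.3, 0.4, 0.8 and 1.7 points. 32 strata minus SAP: −1.2, −1.1, −1.1, −0.8 and +0.2 (paired differences from unrounded values). At 1.3/1.3 and 1.5/1.5 the adjusted gain is 0.5 and 1.1 points with prevalences 20%/10%, and 0.9 and 2.0 with 50%/50%.

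A separately built simulation (5,000 trials per scenario, other assumed prevalences and retained-factor effects) gave gains of 0.5 to 1.9 points for hazard ratios of 1.3 to 1.5, and −0.1 to +0.1 if neither factor is prognostic.

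**Size under the null**, SAP vs adjusted, at 1.0/1.0, 1.3/1.3 and 1.5/1.5: 4.9 vs 5.0%, 4.9 vs 5.1%, 4.8 vs 5.2% (SE 0.13).

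**OS over three looks** (280/342/428 deaths, HR 0.76), SAP vs adjusted, same three scenarios: 79.5 vs 79.5%, 78.3 vs 79.3%, 77.3 vs 79.3%; 32 strata 77.8, 77.4 and 77.3%.

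**What a supportive model would show.** Simulated DFS hazard ratio, SAP vs adjusted: 0.753 vs 0.750 (1.3/1.3); 0.756 vs 0.750 (1.5/1.5). The standard error of log HR is about 2/√377 = 0.103. The shifts are ln(0.753/0.750) = 0.0040 and ln(0.756/0.750) = 0.0080, or 0.04 and 0.08 of a standard error. The adjusted interval is not narrower (standard error ratio 1.001 to 1.002).

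**Information already in the strata.** Without prior chemotherapy, Protocol 4.1.1 requires pT3 or higher, or positive nodes. Every eligible node-negative patient at or below pT2 therefore had chemotherapy, so two of the eight strata (that combination at each PD-L1 level) are homogeneous on this factor.

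**The case for a change.** The strongest case for a change is that the sentence in SAP 4.4 never says it means relative strength, that within-level subgroup hazard ratios do not replace a pooled adjusted effect, and that one Cox model per endpoint costs almost nothing because both factors are in the IxRS. In the simulation the SAP and adjusted 95% intervals disagreed on excluding 1 in 2.3% of trials at 1.3/1.3 and 3.6% at 1.5/1.5 (0.7% if neither factor is prognostic). The power difference also grows with the assumed effects: a small run of 400 trials per scenario with both hazard ratios at 2.0 gave about 4 to 6 points.

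The textual facts stand: the wording is loose and the pooled adjusted effect is not planned. The argument for acting on them does not. The power difference belongs to a different primary test, and nobody proposes replacing the eight-strata log-rank test; a supportive model without alpha recovers none of it. The intervals disagree only in near-borderline trials, where the pre-specified test decides. Hazard ratios of 2.0 would put both omitted factors level with or above the retained ones (assumed 2.0 for nodal status and 1.7 for stage in that run), against the ranking in Protocol 3.3.5. If only node count mattered, at 1.3, the difference is 0.3 points.

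The only related prevalence figures in the documents are neoadjuvant use below 20% (Protocol 1.1.1) and 12% in a European survey (Protocol 3.3.3). These are practice rates, not trial enrolment, but they point towards the 20%/10% scenario (0.5 to 1.1 points) more than towards 50%/50%.

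**Conclusion.** No change follows. Using three of the five factors is a fair trade-off, pre-specified for small strata and anticipated in Protocol 6.4.1. The citation of Protocol 3.3.5 is at most a clerical looseness: that section ranks stage and nodal involvement above the other two, and the SAP nowhere says the omitted factors lack prognostic value. An analyst following SAP 4.4 runs the same test under either reading.

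Followed as written, the plan gives a valid test and a sound conclusion. Both omitted factors are balanced by design, tabulated and examined as subgroups. A covariate-adjusted model is an optional extra that would alter no decision and, at prognostic hazard ratios up to 1.5, would move the expected DFS hazard ratio by about 0.006 at most in the simulated base case. Restoring 32 strata would cost about 1 point of DFS power or break even. These sizes depend on assumed prognostic effects and prevalences. They also leave out the patients enrolled before Protocol version 6, who were stratified on the comorbidity index instead of PD-L1 (SAP 2).

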4.4.1 Primary Efficacy Endpoint

The primary efficacy endpoint is Investigator-assessed DFS, defined as the time from randomization to the first occurrence of a DFS event, defined as any of the following:

- Local (pelvic) recurrence of UC
- Urinary tract recurrence of UC
- Distant metastasis of UC
- Death from any cause

Data for patients without a DFS event will be censored at the last date the patient was assessed to be alive and recurrence free as determined with radiographic evidence. Data for patients with no post-baseline disease assessment will be censored at the randomization date.

For U.S. registrational purposes, the primary efficacy endpoint of DFS will be defined as described above with an additional censoring rule for missed visits. Data for patients with a DFS event who missed two or more consecutive scheduled assessments immediately prior to the DFS event will be censored at the last date the patient was assessed to be alive and recurrence free as determined with radiographic evidence prior to the missed visits or at the randomization date if there is no post-baseline tumor assessment prior to the DFS event.

DFS will be analyzed in the ITT population. The following analyses will be performed for both DFS endpoints described above. Treatment comparisons will be based on the stratified log-rank test at the two-sided level of significance as described in Section 2.2.1. The stratification factors used for the analysis are described in Section 4.4 and the values will be those recorded in the IxRS. The null and alternative hypotheses can be phrased in terms of the survival functions $S_A(t)$ and $S_B(t)$ in Arm A (atezolizumab) and Arm B (observation), respectively:

$$H_0: S_A(t) = S_B(t) \text{ versus } H_1: S_A(t) \neq S_B(t)$$

The HR, λ_A/λ_B , where λ_A and λ_B represent the hazard of experiencing an DFS event in Arm A and Arm B, respectively, will be estimated using a stratified Cox regression model with the same stratification variables used for the stratified log-rank test, and the 95% CI for the HR will be provided. Results from an unstratified analysis will also be provided.

Kaplan-Meier methodology will be used to estimate median DFS for each treatment arm and to construct DFS curves for each treatment arm. The Brookmeyer-Crowley methodology will be used to construct the 95% CI for the median DFS for each treatment arm (Brookmeyer and Crowley 1982).

4.4.2 Secondary Efficacy Endpoints

4.4.2.1 Overall Survival (OS)

Overall survival is defined as the time from randomization to the date of death from any cause, regardless of whether the death occurs during study treatment or following treatment discontinuation. Data for patients who have not died will be censored at the last date they were known to be alive. Data for patients without post-baseline survival information will be censored at the randomization date. Methods for comparison of OS between treatment arms will be the same as the methods for treatment comparison for the primary efficacy endpoint of DFS.

Three analyses of OS are planned (two interim analyses and one final analysis; see Section 2.3.2 for details). The first interim analysis of OS will occur at the time that the primary endpoint of DFS is analyzed. The Type I error control for the secondary endpoint of OS is described in Section 2.2.1.

4.4.2.2 Disease-Specific Survival (DSS)

DSS is defined as the time from randomization to the date of death from UC. Data for patients who have not died will be censored at the last date they were known to be alive. Data for patients who died from causes other than UC will be censored at the date of death. Methods for comparison of DSS between treatment arms will be the same as the methods for treatment comparison for the secondary efficacy endpoint of OS. For the purposes of evaluating DSS, for each patient death, the cause of death will be assessed as related or not related to UC by the investigator.

4.4.2.3 Distant Metastasis-Free Survival (DMFS)

DMFS is defined as the time from randomization to the date of a DMFS event, defined as diagnosis of distant (i.e., non–locoregional) metastasis or death from any cause. Data for patients without a DMFS event will be censored at the last date the patient was assessed to be alive and free of distant metastasis. Data for patients without post baseline disease assessment will be censored at the randomization date. Methods for comparison of DMFS between treatment arms will be the same as the methods for treatment comparison for the primary efficacy endpoint of DFS.

4.4.2.4 Non-Urinary Tract Recurrence-Free Survival (NURFS)

NURFS is defined as the time from randomization to the date of a NURFS event, defined as diagnosis of non-urinary tract (non–UT) recurrence (i.e., pelvic soft tissue or regional lymph node recurrence, or distant metastasis) or death from any cause. Data for patients without a NURFS event will be censored at the last date the patient was assessed to be alive and free of non–urinary tract recurrence. Data for patients with no post baseline disease assessment will be censored at the randomization date day. Methods for comparison of NURFS between treatment arms will be the same as the methods for treatment comparison for the primary efficacy endpoint of DFS.

4.4.3 Exploratory Efficacy Endpoints

4.4.3.1 DFS and OS Analyses by PD-L1 status

To estimate the treatment benefit for patients with different PD-L1 status (IHC score of IC0/1 and IC2/3), the same stratified analysis used for the primary DFS analysis will also be performed for both DFS and OS in ITT patients within each PD-L1 subgroup (IC0/1 and IC2/3), except that PDL1 status as a stratification factor for the primary DFS analysis will not be used for these stratified analysis.

4.4.3.2 Analyses at Landmark Timepoints

The rates of DFS, OS, DSS, DMFS, and NURFS at various timepoints (i.e., every 6 months after randomization) will be estimated by the Kaplan–Meier methodology for each arm and the 95% CI will be calculated using Greenwood’s formula. The 95% CIs for the difference in each of the event rates between the two arms will be estimated using the normal approximation method.

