Additionally, DSS (also known as cancer-specific survival) is a secondary endpoint because non-bladder cancer mortality in this frail and elderly population can be quite significant and may be a competing cause of mortality. After 20 years of post-operative follow-up, the probability of non-tumor-related death was 42% in patients with Stage pT2a/b disease, 40% in pT3a/b, 25% in pT4a/b, and 12% in pTall pN+ (Hautmann et al. 2012), and improvement in DSS in this population may not be reflected in an analysis of OS.

NURFS is included as a secondary endpoint because the impact of urinary tract recurrence on patient survival may be different from non-urinary tract recurrence. Most urinary tract recurrence could be managed by surgical resection (e.g., the majority

of MIBC patients who develop upper urinary tract recurrence can achieve prolonged disease-free survival when treated with radical nephroureterectomy) (Sanderson et al. 2007).

DMFS is also included as a secondary endpoint because distant recurrence is considered to be a major threat to patient survival. Furthermore, this endpoint will be informative as to how atezolizumab adjuvant treatment might affect patterns of recurrence. For MIBC patients post-cystectomy, distant recurrences have been observed to occur more frequently than locoregional recurrences (approximately 20%–50% vs. 5%–15% of cases) (Stein et al. 2001; Shariat et al. 2006).

3.3.2 Rationale for Inclusion of All Patients (All Levels of PD-L1 Expression by IHC) in the Study

This study will enroll patients with muscle-invasive UC of the bladder and upper tract whose tumor specimens are evaluable for PD-L1 expression by IHC as determined by a central laboratory (see [Appendix 3](#)).

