3.3.3 Rationale for Patient Population

The majority of urothelial tumors arise in the bladder, with TCC (also called UC) being the most common histologic subtype. TCC accounts for 90% of all MIBC cases in the industrialized world (Chalasanani et al. 2009). For patients undergoing radical cystectomy alone, recurrence-free survival (RFS) and OS in male and female patients is reported as 66–68% and 58–66% at 5 years and 60–73% and 43–49% at 10 years, respectively (Stein et al. 2001; Hautmann et al. 2003; Madersbacher et al. 2003). In node-positive patients, 10-year DSS and OS rates decrease to 27.7% and 20.9%, respectively (Gschwend et al. 2002).

ESMO, EAU, and NCCN clinical practice guidelines recommend cisplatin-based neoadjuvant chemotherapy prior to cystectomy for MIBC patients based on a meta-analysis which showed a 5% net benefit in 5-year OS (Sternberg et al. 2006). Patients with pT0 or < pT2N0 disease at cystectomy following neoadjuvant chemotherapy were associated with better median survival (13.6 and 12.5 years, respectively). However, median survival (3.4 and 2.4 years, respectively) was very poor for patients with residual

muscle-invasive disease (pT2–4a) or lymph node-positive disease (pN+) following neoadjuvant chemotherapy; there is currently no standard of care for these patients (Sonpavde et al. 2009). Study WO29636 includes MIBC patients with pathological staging of ypT2–4a or ypN+ at cystectomy following neoadjuvant chemotherapy in this trial because this segment of the MIBC patient population has a high unmet medical need.

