2.2.2 Primary Endpoint: Disease-Free Survival

The analysis of the primary endpoint of DFS will take place when approximately 377 DFS events have occurred in the intent-to-treat (ITT) population (defined in Section 4.1.1) and at least 12 months after the last patient is enrolled have elapsed.

The estimated number of events required for the analysis is based on the following assumptions:

- Two-sided, log-rank test at the 0.05 significance level (two-sided)
- 80% power
- 1:1 randomization ratio
- Median DFS for the control (observation) arm of 20 months and estimated median DFS in the atezolizumab arm of 26.7 months (corresponding to a HR of 0.75)
- No interim analysis for DFS

Accrual of the planned 800 patients is projected to occur over 32 months, assuming a ramp-up period of 13 months to a projected accrual rate of 35 patients per month. On the basis of these assumptions, and the projected probability of loss to follow-up for DFS of approximately 32% over 24 months after enrollment, the required number of DFS events is projected to occur at Month 50 from the time the first patient is randomized.

Also on the basis of these assumptions, it is projected that an observed HR of 0.82 or lower will result in a statistically significant difference between treatment arms (i.e., an HR of 0.82 will be the minimally detectable difference at the analysis; this corresponds to an improvement of 4.5 months in median DFS, from 20 months in the control [observation] arm to 24.5 months in the atezolizumab arm).

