4.5.2 Adverse Events

Verbatim descriptions of adverse events will be mapped to Medical Dictionary for Regulatory Activities (MedDRA terms). Treatment emergent events (defined as events occurring on or after the first dose of atezolizumab, or, for patients in the observation arm, after the date of randomization) will be summarized by MedDRA term, appropriate MedDRA levels, and NCI CTCAE (National Cancer Institute, Common Terminology Criteria for Adverse Events) v4.0 grade. For each patient, multiple occurrences of the same event will be counted once at maximum severity reported will be used in the summaries. Adverse events will be summarized regardless of relationship to study drug as assessed by the investigator. All adverse events, adverse events leading to withdrawal of study drug, adverse events leading to dose interruption, Grade ≥ 3 adverse events, serious adverse events, adverse events related to study drug, adverse events of special interest, and immune-mediated adverse events will be summarized. Deaths and cause of death will be summarized.

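### Low priority: the DSS landmark rates in SAP 4.4.3.2 are net of other-cause death; a cumulative incidence of UC death could be reported beside them

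*SAP*

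**What the plan says.** The DSS rule in SAP 4.4.2.2 is: "Data for patients who died from causes other than UC will be censored at the date of death". Protocol 6.4.2.2 has the same rule.

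SAP 4.4.3.2, which sits under the exploratory efficacy endpoints, includes DSS in its list: "The rates of DFS, OS, DSS, DMFS, and NURFS at various timepoints (i.e., every 6 months after randomization) will be estimated by" Kaplan-Meier, with Greenwood intervals by arm. It continues: "The 95% CIs for the difference in each of the event rates between the two arms" will come from a normal approximation. Protocol 6.8.1 also uses Kaplan-Meier for DSS landmark rates.

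Protocol 3.3.1 gives the reason for having DSS: "non-bladder cancer mortality in this frail and elderly population can be quite significant and may be a competing cause of mortality". It adds that a gain in DSS might not show in OS.

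Neither document plans a cumulative incidence function or any other competing-risks estimate. The only other cause-of-death output is in SAP 4.5.2: "Deaths and cause of death will be summarized". That is a count in the safety population, grouped by treatment received, and has no time axis.

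**The concern.** DSS is the only one of the five landmark endpoints that censors some deaths. OS, DFS, DMFS and NURFS all count death from any cause, so one minus their Kaplan-Meier rate is the proportion of patients expected to have had the event. For DSS the same calculation gives the probability of UC death in a setting where nobody dies of anything else, and it needs independence between the causes even for that reading. When other-cause deaths occur, it exceeds the proportion who actually die of UC.

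The DSS rates will be reported in the same list as the other four with no label to mark the difference, and nothing in the plan supplies the absolute figure. What is at stake is how a secondary endpoint is read on the absolute scale.

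**Working it through.** **Plan's own figures.** The documents state no DSS figure. The nearest is the OS design, which reproduces. With HR = 34/44.7, the Schoenfeld formula gives 420 events for a fixed design. With Lan-DeMets O'Brien-Fleming looks at 280, 342 and 428 deaths, the two-sided boundaries are 0.0112, 0.0210 and 0.0422 and power is about 80%, matching SAP 2.3.2. The OS hazards are therefore a sound starting point.

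**Other-cause hazard (assumed).** Protocol 3.3.3 offers an anchor: "In node-positive patients, 10-year DSS and OS rates decrease to 27.7% and 20.9%, respectively". Under independence, net other-cause survival at 10 years is 0.209/0.277 = 0.75. So o = -ln(0.209/0.277)/120 = 0.00235 per month, or 2.8% a year. The series is node-positive only, so this is an anchor and not a bound.

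**Model.** Net of other-cause death:
- recurrence-free: D(t) = π + (1-π)exp(-rt)
- alive after recurrence, with UC-death hazard p: P(t) = (1-π) r [exp(-rt) - exp(-pt)]/(p-r)
- the hazard o applies in both states.

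The parameters solve D(20)exp(-20o) = 0.50 (control DFS median 20 months), [D(34)+P(34)]exp(-34o) = 0.50 (control OS median 34 months) and [D(120)+P(120)]exp(-120o) = 0.209. The solution is π = 0.273, r = 0.0532 and p = 0.0763, with net 10-year DSS 0.277.

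**Two quantities at time T.** One minus Kaplan-Meier estimates 1 - [D(T)+P(T)]. The cumulative incidence of UC death is the integral from 0 to T of p·P(t)·exp(-ot). For the atezolizumab arm, D is replaced by D raised to 0.75, with the same p and o, and P is recomputed.

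| Months | Control 1-KM | Control cumulative incidence | Gap | Between-arm difference, 1-KM | Between-arm difference, cumulative incidence | Excess |
|---|---|---|---|---|---|---|
| 24 | 32.5% | 31.5% | 1.0 | 6.5 | 6.3 | 0.2 |
| 36 | 48.0% | 46.0% | 2.1 | 8.7 | 8.4 | 0.3 |
| 60 | 64.5% | 60.8% | 3.8 | 10.2 | 9.7 | 0.5 |

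Gaps are taken before rounding. If treatment has no effect on UC and o is equal in both arms, the excess is zero.

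**Sensitivity, control-arm gap at 24, 36 and 60 months.**
- o halved or doubled, with 10-year OS held at 20.9%: 0.5-1.8, 1.1-3.6 and 2.0-6.3 points. The between-arm excess is 0.1-0.4, 0.2-0.6 and 0.2-1.0.
- No cure fraction, same o: 1.0, 2.2 and 4.9.
- Cruder still, a constant other-cause share of deaths of 12% to 42%, with h = ln2/34 and u = h(1-share), comparing 1-exp(-uT) with (u/h)(1-exp(-hT)): 0.9-2.3, 1.8-4.5 and 3.8-9.9. The shares borrow the 20-year range in protocol 3.3.1, from 12% in node-positive patients up to "the probability of non-tumor-related death was 42% in patients with Stage pT2a/b disease". They were not reported as shares of deaths.

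**Unequal other-cause hazards.** Suppose o is 1.5 times higher on atezolizumab (an assumption with no source in the documents). The 60-month difference is then 10.2 points by Kaplan-Meier and 11.3 by cumulative incidence, so Kaplan-Meier understates it. With no UC effect at all, Kaplan-Meier shows 0, while cumulative incidence shows 0.5, 1.0 and 1.8 points at the three landmarks.

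**Scale and timing.** With 400 patients per arm and no censoring, the 95% half-width of the difference, 1.96 × sqrt(sum of p(1-p)/400) with p here the UC-death probability in each arm, is 6.3 points at 24 months and about 6.8 at 36 and 60. On timing, SAP 2.2.2 states: "Accrual of the planned 800 patients is projected to occur over 32 months". At Month 50 a patient reaches 24 months if enrolled by Month 26, and 36 months if enrolled by Month 14; nobody reaches 60. At Month 63 only patients from the first 3 months reach 60. At Month 95 everyone can, since 95 - 32 = 63.

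**The case against.** The best defence is that the plan does what the protocol set out to do. Protocol 3.3.1 wants DSS because other-cause death can hide a UC effect in OS, and censoring other-cause deaths follows from that aim. A cumulative incidence is itself lowered by other-cause death, so it answers a different question. This stands. A reader might infer that the plan contradicts its own rationale, or that Kaplan-Meier is the wrong estimator for DSS. The documents support neither: the planned rate is a legitimate net quantity, and the proposal is a second quantity beside it.

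It is also fair that no section presents these rates as absolute risk, so any harm depends on how a reader takes them. The landmarks are exploratory and DSS is outside type I error control. At Month 50 the usable landmark is mainly 24 months, where the illustrative between-arm excess is 0.2 points against a half-width of 6.3.

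Finally, the model fits four parameters to four figures, so nothing tests its fit. It also joins a historical node-positive series to this trial's design medians. The numbers show direction and rough size only.

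**Conclusion.** The omission is clear from the text: the only time-based UC-death rates planned are net of other-cause death. This is an optional improvement and not an error in a planned analysis.

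The control-arm gap of about 1, 2 and 4 points (about 0.5-2, 1-4 and 2-6 with the hazard halved or doubled) rests on an assumed other-cause hazard and on independence between causes. The small between-arm excess rests further on equal other-cause hazards in the two arms. One should not infer that Kaplan-Meier always overstates the difference slightly: if treatment changed other-cause mortality, the bias could change sign, and the Kaplan-Meier DSS rates could not show it.

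Nor should a reader infer a problem with the DSS comparison itself. The stratified log-rank test and the Cox hazard ratio compare cause-specific hazards and remain valid. Alpha, sample size and the primary conclusion do not change.

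**What to change.** In SAP 4.4.3.2, add Aalen-Johansen estimates of the cumulative incidence of death from UC and of death from other causes, by arm in the ITT population at the same landmarks, with 95% intervals by arm and for the between-arm difference. Label the Kaplan-Meier DSS rates as net of other-cause death, and use the cumulative incidence for any statement of absolute UC-death risk. Showing both causes also reveals any imbalance in other-cause mortality. Leave the log-rank and Cox analyses of DSS as they are.

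The cost is one extra table. No new data are needed, because SAP 4.4.2.2 already has the investigator classify each death as related to UC or not.

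One editorial item: the DSS sentence in protocol 6.4.3 censors patients without an event when last known alive and free of UC, which conflicts with protocol 6.4.2.2 and SAP 4.4.2.2. SAP sections 1 and 4.9 make the SAP rule govern, so no analysis changes. The wording can be aligned at the next amendment and does not need one of its own.
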